Appendix I
Percent of Normal Bone Marrow Irradiated Using Standard Radiation Ports

Anatomic Site	% of Total Red Marrow
Head	13.1
Cranium	11.9
Mandible	1.2
Upper Limb Girdle	8.3
2 Humeri (head and neck)	1.9
2 Scapulae	4.8
2 Clavicles	1.6
Sternum	2.3
Ribs	7.9
Vertebrae	42.3
Cervical	3.4
Thoracic	14.1
Lumbar	10.9
Sacrum	13.9
Lower Limb Girdle	26.1
2 Os Coxae	22.3
2 Femoral heads and necks	3.8

Adapted from: Ellis R.E. The distribution of active bone marrow in the adult. *Phys Med Biol* 5:255, 1961.

Appendix II

Patient Nintedanib Capsule Diary

Subject ID # _____

Subject Initials _____

Cycle # _____

Date	Study Day	Morning dose	Evening dose	Comments ¹
	1			
	2			
	3			
	4			
	5			
	6			
	7			
	8			
	9			
	10			
	11			
	12			
	13			
	14			
	15			
	16			
	17			
	18			
	19			
	20			
	21			
	22			
	23			
	24			

	25			
	26			
	27			
	28			

¹Changes to concomitant medications can be written in the comment section.

Patient _____ **Reviewer** _____

Appendix V
Specimen Tissue Transmittal Form
Biomarker Flow Sheet

Phase II evaluation of Nintedanib (BIBF 1120) in the treatment of bevacizumab-resistant persistent or recurrent epithelial ovarian, fallopian tube, or primary peritoneal carcinoma.

Insert copy of this completed form with shipment and fax to
ATTN: DUKE – BIOMARKER at [contact]

Section 1: General Information					
SUBJECT INITIALS		SUBJECT STUDY ID #		SITE NAME	Duke

Section 2: Flow sheet					
DATE OF BIOMARKERS DRAWN		CYCLE #		DAY #	

EVENT	TIME DRAWN	TIME FROZEN	NUMBER OF CRYOVIALS	COMMENTS	INITIALS
Whole blood			N/A		
Serum					
Plasma – EDTA					
Plasma – citrate					
Urine					

Signature: _____

Initials: _____

Section 3: Shipment Information (for DUMC site, complete transfer log)
--

DATE SHIPPED: _____

TRACKING NUMBER OF SHIPMENT: _____

NAME OF PERSON RESPONSIBLE FOR SHIPMENT: _____

PHONE NUMBER OF PERSON RESPONSIBLE FOR SHIPMENT: _____

Appendix VI
Specimen Tissue Transmittal Form
Paraffin-Embedded Tumor

Phase II evaluation of Nintedanib (BIBF 1120) in the treatment of bevacizumab-resistant persistent or recurrent epithelial ovarian, fallopian tube, or primary peritoneal carcinoma.

Insert copy of this completed form with shipment and fax to
ATTN: DUKE – [name] at [contact]

Section 1: General Information					
SUBJECT INITIALS		SUBJECT STUDY ID #		SITE NAME	

Section 2: Flow sheet					
-----------------------	--	--	--	--	--

EVENT	PARAFFIN-EMBEDDED PRIMARY TUMOR	PARAFFIN-EMBEDDED METASTATIC TUMOR	COMMENTS	INITIALS
DATE TISSUE INITIALLY OBTAINED				
INDICATE TISSUE BLOCK (TB) OR UNSTAINED SLIDES (US)				

If the specimen was not collected please indicate reason: (e.g., patient refused, not enough tumor for research, referring site won't release tumor). _____

Signature: _____

Initials: _____

Section 3: Shipment Information (for DUMC site, complete transfer log)
--

DATE SHIPPED: _____

TRACKING NUMBER OF SHIPMENT: _____

NAME OF PERSON RESPONSIBLE FOR SHIPMENT: _____

PHONE NUMBER OF PERSON RESPONSIBLE FOR SHIPMENT: _____

APPENDIX VII
Protocol Deviation Form
Protocol BIBF 1120

Subject ID Number: _____

Complete a new form for each deviation from the protocol.

Date of Protocol Deviation (DD/MMM/YYYY): _____ / _____ / _____

Description of Protocol Deviation:

Reason for Protocol Deviation:

What steps were taken to resolve this Protocol Deviation and prevent recurrence:

Does this deviation meet Duke IRB reporting requirements: NO Yes

COMPLETED BY: _____ / _____ / _____
(DD/MMM/YYYY)

Investigator's Signature: _____ / _____ / _____
(DD/MMM/YYYY)

Date Submitted To: _____ (DD/MMM/YYYY)

Duke IRB _____ / _____ / _____

APPENDIX IX

Study #: Pro00033060	Subject ID #:		
Inclusion Criteria	Yes	No	N/A
Patient signed approved Informed Consent & Authorization Form permitting release of personal health information.			
Patient is at least 18 years of age.			
Patient has recurrent/persistent: Epithelial Ovarian, Fallopian Tube, or Primary Peritoneal Carcinoma. • Histologic documentation of the original primary tumor is required via the pathology report. The following histologic epithelial cell types are eligible: Serous, endometrioid, mucinous, or clear cell adenocarcinoma; Undifferentiated, mixed epithelial or transitional cell carcinoma; Brenner's Tumor; Adenocarcinoma N.O.S.			
Patient is Bevacizumab-resistant: treatment-free interval following response to Bevacizumab (CR/PR/SD) of < 6 months, or progressed during treatment with Bevacizumab-containing therapy.			
Patient has either measurable disease, per RECIST 1.1 (at least 1 lesion, accurately measured in at least 1 dimension) or detectable (non-measurable) disease (CA125>2x ULN + either ascites/pleural effusion attributed to tumor OR solid/cystic abnormalities that do not meet RECIST 1.1) • For patients with measurable disease: • Each lesion must be \geq 10 mm when measured by CT, MRI, or caliper measurement by clinical exam. • Each lesion must be \geq 20 mm when measured by chest x-ray. • Lymph nodes must be $>$ 15 mm in short axis when measured by CT or MRI.			
For patients with measurable disease: patient has at least 1 target lesion (RECIST 1.1) to be used to assess response on this protocol. • Tumors in irradiated fields are non-target unless: progression documented, or biopsy confirms persistence \geq 90 days after completion of radiation.			
Patient has an ECOG Performance status of 0 or 1.			
Patients is free of active infection requiring antibiotics (Exception: Uncomplicated UTI).			
Patient has recovered from effects of recent surgery, radiotherapy, or chemotherapy.			
If patient had hormonal therapy directed at malignant tumor: discontinued \geq 1 week before registration. • Continuation of hormone replacement therapy is permitted.			
If patient had therapy directed at malignant tumor (ex: immunologic agents): discontinued \geq 3 weeks before registration.			
If patient received prior therapy with Bevacizumab: \geq 4 weeks between discontinuation and treatment on this study.			
Patient has had 1 prior platinum-based chemotherapeutic regimen for management of primary disease containing Carboplatin/Cisplatin/organoplatinum compound. May have included intraperitoneal therapy/high-dose therapy/consolidation/non-cytotoxic agents/biologic therapy/extended therapy administered after surgical/non-surgical assessment			
Patients are allowed to receive, but are not required to receive, two additional cytotoxic regimens (a total of 3 cytotoxic regimens) for management of recurrent or persistent disease. Patients who have received only one prior cytotoxic regimen (platinum-based regimen for management of primary disease), must have a platinum-free interval of less than 12 months, or have progressed during platinum-based therapy, or have persistent disease after a platinum-based therapy.			
Patients must NOT have received any non-cytotoxic therapy for management of recurrent or persistent disease other than bevacizumab-containing regimens. Patients are allowed to receive, but are not required to receive, biologic (non-cytotoxic) therapy as part of their primary treatment regimen.			
Patient has adequate bone marrow function: • Absolute Neutrophil Count \geq 1,500/mcl (equivalent to CTCAE v4.0 grade 1). • Platelets \geq 100,000/mcl. • Hemoglobin \geq 9.0 g/dL.			
Patient has adequate renal function: • Creatinine \leq 1.5 x institutional upper limit of normal (equivalent to active version of NCI AE grade 1).			
Patient has adequate hepatic function: • Bilirubin is within normal limits (CTCAE v4.0 grade 1). • ALT/AST \leq 1.5 x ULN (CTCAE v4.0 grade 1). If patient has liver metastases: ALT/AST \leq 2.5 x ULN. • Alkaline phosphatase \leq 2.5 x ULN (CTCAE v4.0 grade 1).			

Patient has adequate neurologic function: • Neuropathy (sensory and motor) \leq CTCAE v4.0 grade 1.			
Patient has adequate blood coagulation: • Prothrombin: International Normalized Ratio $< 1.5 \times$ ULN & Partial Thromboplastin Time $< 1.5 \times$ ULN. • Prophylactic/low molecular weight Heparin (ex: Enoxaparin) is allowed (Exception: Warfarin is not allowed).			
If patient is of child-bearing potential: negative serum pregnancy test prior to study entry and be willing to practice an effective form of contraception up until three months after of receiving the last drug treatment..			
If patient had major surgical procedure/open biopsy/significant traumatic injury: > 28 days before 1st day of treatment.			
If patient has undergone a core biopsy/IV Port placement: > 7 days prior to 1st date of study therapy.			
Study #: Pro00033060	Subject ID #:		
	Exclusion Criteria	Yes	No
Patient is breastfeeding or pregnant.			
Patient had previous treatment with Nintedanib.			
Patient received radiation to $> 25\%$ of marrow-bearing areas. • Head: 13.1% (Cranium: 11.9%, Mandible: 1.2%) • Upper Limb Girdle: 8.3% (2 Humeri {head and neck}: 1.9%, 2 Scapulae: 4.8%, 2 Clavicles: 1.6%) • Sternum: 2.3% • Ribs: 7.9% • Vertebrae: 42.3% (Cervical: 3.4%, Thoracic: 14.1%, Lumbar: 10.9%, Sacrum: 13.9%) • Lower Limb Girdle: 26.1% (2 Os Coxae: 22.3%, 2 Femoral heads and necks: 3.8%)			
Patient has history of other invasive malignancies, & there is evidence of malignancy being present within last 3 years. Exception: Non-melanoma skin cancer.			
Patient's previous cancer treatment contraindicates this protocol therapy.			
Patient received prior radiotherapy to any portion of abdominal cavity/pelvis. Exception: Treatment of Ovarian, Fallopian Tube, or Primary Peritoneal Cancer within last 3 years. Exception: For localized cancer of breast/head & neck (Exception: CNS disease)/skin, if completed > 3 years before registration & patient remains free of recurrent/metastatic disease.			
Patient received prior chemotherapy for any abdominal or pelvic tumor. Exception: Ovarian/Fallopian Tube/Primary Peritoneal Cancer or localized Breast Cancer within last 3 years. Exception: Adjuvant chemotherapy for localized Breast Cancer, if completed > 3 years before registration & patient remains free of recurrent/metastatic disease.			
Patient has a history of abdominal or tracheal-esophageal fistula, or gastrointestinal perforation.			
Patient has a history of intra-abdominal abscess within 6 months of enrollment.			
Patient has a serious, uncontrolled, concomitant disorder (such as diabetes mellitus).			
Patient has clinically significant cardiovascular disease, including: • Uncontrolled hypertension: systolic > 150 mm Hg or diastolic > 90 mm Hg. • Unstable angina, or they had a myocardial infarction within the past 6 months prior to registration. • NYHA grade II or greater congestive heart failure. • Serious cardiac arrhythmia requiring medication (Exception: Asymptomatic atrial fibrillation with controlled ventricular rate.) • Peripheral vascular disease/Peripheral ischemia \geq CTCAE v4.0 grade 2			
Patient has a serious non-healing wound, ulcer, or bone factor. Exception: Granulating incisions healing by secondary intention with no evidence of fascial dehiscence or infection. Weekly wound examinations are required.			
Patient has active bleeding/pathologic condition with high risk of bleeding, such as: bleeding disorder/coagulopathy/tumor involving major vessels.			
Patient has history/evidence upon physical exam of CNS disease; seizures not controlled with standard medical therapy; brain metastases; or history of CVA/TIA/subarachnoid hemorrhage within 6 months of 1st date of treatment on this study.			
Patient has been diagnosed with primary brain tumors within the last 3 years.			
Patient has central pulmonary metastases, or recent hemoptysis ($\geq 1/2$ tsp. of red blood) within 28 days of registration.			
Patient has clinically significant proteinuria ($>$ Grade 1), or UPC ratio above 1.0.			

Patient is suspected of having transmural tumor bowel involvement (per investigator's discretion).			
Patient has clinical symptoms/signs of gastrointestinal obstruction, and requires parenteral hydration and/or nutrition.			
Patient is on therapeutic doses of anticoagulants, or is taking Warfarin.			

Signature of Coordinator/Research Nurse

Date:

Signature of Investigator/Sub-Investigator

Date:

APPENDIX X

Subject Registration Form

Section 1: SUBJECT INFORMATION

First Initial: _____ Middle Initial: _____ Last Initial: _____

Sex: Male Female Date of Birth: ____ / ____ / ____ Duke MRN (if applicable): _____

Date Consent Signed: ____ / ____ / ____ Version Date of Site Consent: ____ / ____ / ____

Type of Cancer Diagnosis: _____ Protocol Name: _____

RACE:

White
 Black or African American
 Native Hawaiian or other Pacific Islander
 Asian
 American Indian or Alaska Native
 Not Reported
 Unknown

ETHNICITY:

Hispanic or Latino
 Non Hispanic or Latino
 Not Reported
 Unknown

Section 2: SITE INFORMATION

Site Name: _____ Site Fax #: _____

Study Coordinator Name: _____ Phone #: _____ Pager #: _____

Study Coordinator Email: _____

Treating MD Name: _____ Phone #: _____ Pager #: _____

Treating MD Email: _____

Section 3: ELIGIBILITY

Subject meets all eligibility criteria. (Please note: If subject meets all eligibility criteria, please provide completed eligibility checklist along with supporting source documentation to the Duke Team.)

Date of expected Cycle 1 Day 1: ____ / ____ / ____

Subject does not meet all eligibility criteria.

If subject does not meet eligibility, please explain below.

Study Coordinator Signature: _____ Date: _____

Section 4: TO BE COMPLETED BY DUKE STUDY TEAM

Subject Study Number		Cohort Number	N/A
----------------------	--	---------------	-----

Duke Investigator Signature and Date: _____

Appendix XI

Rank Preferences and Relative Concern Exercises

When researchers are testing new treatments for ovarian cancer, they have to decide ahead of time what kind of results they want to measure. We would like to find out what kind of results patients think are most important. Some of the outcomes researchers measure are listed below, with descriptions of what they mean.

Overall quality of life. This means how you are doing overall. It includes your physical and emotional well-being and how well you can perform your normal daily activities.

Side effects from treatment. This means health effects that are caused by your cancer treatment. Examples of common side effects of cancer treatment are hair loss, neuropathy or numbness or tingling in your fingers and toes, nausea and vomiting.

Symptoms from cancer. Some common symptoms of ovarian cancer are abdominal fullness, pain or bloating, constipation, loss of appetite, and nausea.

Progression-free survival. This is the average length of time that a woman will spend without any sign of her cancer growing or coming back once she starts a new treatment.

Overall survival. This is the average length of time that a woman will live after starting a new treatment.

A. Relative Concern Exercise

Now please indicate below how concerned you are about each of the following outcomes of your treatment.

Quality of life	Not concerned	A little bit concerned	Moderately concerned	Very concerned	Deeply concerned
Symptoms of cancer	Not concerned	A little bit concerned	Moderately concerned	Very concerned	Deeply concerned
Side effects of treatment	Not concerned	A little bit concerned	Moderately concerned	Very concerned	Deeply concerned
Progression-free survival	Not concerned	A little bit concerned	Moderately concerned	Very concerned	Deeply concerned
Overall survival	Not concerned	A little bit concerned	Moderately concerned	Very concerned	Deeply concerned

B. Rank Preferences

Please rank the following outcomes we can measure in order from the MOST important (1) to the LEAST important (5) to you.

_____ Overall quality of life. This includes your physical and emotional well-being and how well you can perform your normal daily activities.

_____ Side effects that are caused by the treatment.

_____ Symptoms that are caused by ovarian cancer.

_____ Length of time spent without the cancer growing.

_____ Total length of life remaining.

(To avoid any potential bias introduced associated with the order the concepts are listed, the order will be randomized across participants.)

C. Token distribution exercise

Now imagine that you have 100 coins or tokens. We would like you to distribute the tokens to indicate how important each outcome is to you. You could place all 100 tokens on one outcome if you only care about that outcome. If you feel that all the outcomes are equally important, you will place 20 tokens on each outcome.

_____ Overall quality of life. This includes your physical and emotional well being and how well you can perform your normal daily activities.

_____ Side effects that are caused by the treatment.

_____ Symptoms that are caused by ovarian cancer.

_____ Length of time spent without the cancer growing.

_____ Total length of life remaining.

(To avoid any potential bias introduced associated with the order the concepts are listed, the order will be randomized across participants.)

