The proposed pilot study will query women with ovarian cancer about their preferences for the possible effects of treatments on (1) progression-free survival, (2) overall survival, (3) development of severe side effects, (4) overall quality of life, and (5) ovarian-cancer specific health symptoms. This study will allow us to determine the feasibility of assigning patient-determined weights to different individual endpoints for the future construction of a patient-centered composite endpoint. Because preferences are often sensitive to the method of elicitation, multiple methods of elicitation will be used to assess the robustness of preferences. Baseline quality of life and symptom index elicitation will allow examination of subjects' preferences in relation to their current symptoms and well being.

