11. See section 7.3 for specimen requirements. Collect whole blood, serum, plasma, and urine pre-cycle #1, every other cycle (i.e. Cycle 3, 5, etc.), at the time of progression, and one month after study treatment is discontinued.
12. Repeat every other cycle and more frequently as clinically indicated. For patients with hepatic injury or elevated liver function tests repeat the INR/PT/PTT every cycle until the liver function tests return to baseline; then resume INR/PT/PTT every other cycle.
13. Repeat every other cycle and more frequently as clinically indicated.
14. Only for subjects enrolled at Duke

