Secondary Aim 3 is to estimate the distribution of PFS and overall survival (OS). PFS was defined above. OS is defined as the length of the interval from on-study to death due to any cause. Both PFS and OS will be estimated with the Kaplan-Meier curve. In addition, we will compare the PFS of patients who had prior bevacizumab resistance with that of patients who had prior bevacizumab and chemotherapy resistance. Specifically, within each of these two groups, we will describe PFS with a Kaplan-Meier curve and the 6-month PFS rate (with its 80% confidence interval). We expect the latter group to have worse PFS than the former.

Secondary Aim 4 is to elicit patient preferences for outcomes of ovarian cancer treatment. The distribution of rank preferences for each general attribute will be described using mean ranks as well as the proportions of times each concept was ranked as most

important, second most important, third most important, fourth most important, and least important. In the token ranking exercise, to describe the allocations of tokens across the general attributes, we will report means, standard deviations, and median numbers of tokens for each attribute. To examine consistency between token allocations with rank preferences, we will reverse order the rank preferences such that higher ranks correspond to higher preferences and compute correlation coefficients. We will test whether correlations between ranks and token counts differ between attributes using Spearman rank tests. We will also examine the proportion of patients who provided the highest token counts to their most preferred attribute and vice versa. In the ratings exercise, to describe respondents' ratings on the 5-point Likert scale representing level of concern with each attribute included in the DCE, we will report frequencies of ratings for each attribute as well as means to provide a summary measure.

Secondary Aim 5 is to characterize baseline quality of life and cancer-related symptoms. We will use descriptive characteristics to summarize baseline characteristics for the study cohort enrolled at Duke. These characteristics will include summary scores from the NFOSI-18 and the FACT-GOG-Ntx. We will report means, medians, and standard deviations for continuous variables and counts and proportions for categorical variables.

Statistical Analysis of Translation Research Objectives

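### Appendix XI randomizes the order of the five outcomes in exercises B and C but states no randomization for rating exercise A

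*Combined protocol and SAP*

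**What the plan says.** Appendix XI contains three exercises on the same five outcomes: quality of life, symptoms of cancer, side effects of treatment, progression-free survival and overall survival.

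- **Exercise A (rating).** "Now please indicate below how concerned you are about each of the following outcomes of your treatment". Each outcome has its own five-category scale. The printed order is quality of life, symptoms, side effects, progression-free survival, overall survival. No instruction on order accompanies it.
- **Exercise B (ranking).** "Please rank the following outcomes we can measure in order from the MOST important (1) to the LEAST important (5) to you". The list is followed by a note: "To avoid any potential bias introduced associated with the order the concepts are listed, the order will be randomized across participants".
- **Exercise C (tokens).** "Now imagine that you have 100 coins or tokens". The same note is printed again after this list.

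Section 11 (Secondary Aim 4) says of the ratings: "we will report frequencies of ratings for each attribute as well as means to provide a summary measure". It has no term or adjustment for list position. Section 2.7 explains why there are several exercises: "Because preferences are often sensitive to the method of elicitation, multiple methods of elicitation will be used to assess the robustness of preferences". Under Section 7.1, note 14, the preference tasks are completed as follows: "Only for subjects enrolled at Duke". The number of such patients is not given.

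**The concern.** The protocol accepts that list order can bias answers about these outcomes, protects two of the three exercises against it, and gives no reason for leaving out the third.

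If every patient meets A in the printed order, any tendency to rate early rows differently from late rows falls on the same outcome in every patient. Quality of life would always be first and overall survival always last. Two things are at stake. One is the comparison of A's summaries between outcomes, which any reader of a table of five means will make. The other is the robustness comparison described in Section 2.7: with order randomized in B and C but constant in A, a difference between A and the others has two possible explanations, the elicitation method and the list position.

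The point concerns the order of items within exercise A. It does not concern the order in which the three exercises are given.

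**Working it through.** The plan gives no figure to reproduce. The check is first textual, then structural.

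**1. The exercises side by side.**

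| Exercise | Task | Order-randomization note | Planned summary (Section 11) |
|---|---|---|---|
| A | Rate each outcome on a 5-point scale | None | Frequencies and means per outcome |
| B | Rank 1 to 5 | Yes, after the list | Mean ranks, proportion at each rank |
| C | Distribute 100 tokens | Yes, after the list | Means, SDs, medians |

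Nothing in Section 2.7, Section 7.4 or Section 11 extends the note to A.

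**2. Is outcome separable from position?** Write a patient's rating of outcome *j* shown in position *k* as

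rating = μ + α(*j*) + β(*k*) + error.

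With five outcomes and five positions there are 1 + 4 + 4 = 9 free parameters.

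- *One order for all:* *k* = *j* in every row, so the four position columns of the design matrix duplicate the four outcome columns. The rank is 1 + 4 = 5. Computed rank: 5 at n = 10, 27 and 56.
- *Order randomized between patients:* computed rank 9 of 9 in one simulated randomization at each of n = 10, 27 and 56.

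The values of n are assumptions, because the number of Duke patients is not stated; 27 and 56 are the trial's stage 1 and total sizes. The rank under one order is the same at each, so more patients do not help.

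**3. What the planned means would estimate.** With one order, the mean for outcome *j* estimates μ + α(*j*) + β(*j*). The first-minus-last difference therefore estimates

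[α(1) − α(5)] + [β(1) − β(5)],

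and A's data cannot divide it into its two parts. With randomized order every outcome has the same expected position effect, the average of the five β values, and this cancels from every difference.

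**4. Scale, as an assumption only.** Suppose ratings drift by *d* points per row. The first-to-last difference shifts by 4*d*:

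| Assumed *d* | Shift, one order (4*d*) | Expected shift, randomized |
|---|---|---|
| 0.05 | 0.20 | 0 |
| 0.10 | 0.40 | 0 |
| 0.20 | 0.80 | 0 |

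The documents support no value of *d*, including zero. The table shows how a drift would carry through and does not estimate one. The zero in the last column covers position within A's table only.

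**The case against.** **The fixed order is not stated.** B and C are also printed in one order although they are to be shuffled, so a printed order proves nothing. This stands. The evidence is the absence of a note that the other two exercises both carry, and the point is therefore conditional on A being given as printed. Staff who follow the text have no instruction to do otherwise.

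**A is a different kind of task.** Ranking and token allocation force a trade-off between outcomes. In A all five can receive the same rating, so leaving A out may have been deliberate, and a position effect may well be smaller there. This also stands as a reason for modesty. It does not show that the effect is absent, and the documents do not give it as their reason.

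**No between-outcome contrast is planned for A.** Correct. Section 11 plans summaries of A outcome by outcome, and its formal consistency analyses use ranks and tokens, where order is randomized. A reader might infer that the comparison of quality of life with survival, or the weights for a future composite endpoint, would be distorted. The documents do not support that. Section 2.7 describes a pilot of whether patient-determined weights are feasible, and nothing says that A's means supply them.

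**B and C offer some protection.** In part. A preference seen only in A would lack support from B and C. They cannot estimate A's position effect, however, and so cannot show why A differed.

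**Shuffling A does not remove every order effect.** Correct. Before A, patients read a list of definitions that also runs from quality of life to overall survival and carries no randomization note.

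**Conclusion.** The point holds in a limited form. Appendix XI states order randomization for B and C and none for A. If A is given as printed, outcome and list position are completely aliased in its planned summaries (rank 5 of 9, whatever the sample size), and a disagreement between A and B or C could not be attributed to elicitation method alone.

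A reader might go further and conclude that the ratings will be biased by a known amount or number of standard errors. The documents give no position effect, no rating SD, no correlation between ratings and no number of Duke respondents, so no such size can be derived. The aliasing follows from the structure; the bias is only a possibility.

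The consequence is small. Secondary Aim 4 is descriptive and confined to Duke patients. The primary endpoint and the two-stage design are unaffected. This is a worthwhile improvement rather than a necessary correction.

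**What to change.** Extend the note already printed for exercises B and C to exercise A, so that the rows of A are also shuffled between patients, and record on the form the order each patient saw. Preferably do the same for the definitions list that precedes A, since shuffling A alone removes only position effects within its own table.

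If a single order for A is intended, say so in Appendix XI and state in Section 11 that A's means are not to be compared between outcomes.

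The cost is a sentence or two in Appendix XI, and slightly more form handling and data entry. Shuffled forms are already needed for B and C, and no extra patients or visits are required.
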